307 source of such bias is the application of a differential threshold for resuscitation by paramedics assigned to different
308 airway management strategies, since they will not be blinded. We will use several strategies to prevent this bias from
309 occurring, to detect it if it happens, and to correct it if necessary (see sections 4.4.2 and 5.3.7 for details).

310

311 **4.3.2 Performance bias (systematic differences between groups in the care that is provided, or in exposure to** 312 **factors other than the interventions of interest).**

313

314 This bias will be minimised by:

315

- 316 • defining the intervention and comparator, as well as standard protocols for other procedures undertaken
317 during the trial (see sections 4.5 and 5.11);
- 318 • blinding staff beyond ED (section 5.2.2) to method of initial airway management (see section 5.2.2) and
319 assessing the success of blinding (see section 5.2.2);
- 320 • monitoring adherence to the protocol (see section 7.1 and 7.2).
321

322 **4.3.3 Detection bias (systematic differences between groups in how outcomes are determined)**

323

324 This bias will be minimised by:

325

- 326 • using an objective primary outcome measure (modified Rankin Scale, see section 5.6);
- 327 • blinding individuals assessing outcomes (see section 5.2.2).
328

329 **4.3.4 Attrition bias (systematic differences in the availability of outcome data between groups)**

330

331 This bias will be minimised by:

332

- 333 • obtaining almost complete follow-up. About 90% of patients will not survive to hospital discharge. We
334 expect to be able to account for all other patients who consent to follow-up from the time of discharge up to
335 six months
336

337 **4.3.5 Reporting bias**

338

- 339 • This type of bias will be minimised by having pre-specified outcomes (see section 4.6) and a pre-specified
340 analysis plan (see section 6).
341

342 **4.4 Trial population**

343

344 Adults who have suffered an OHCA that is not due to trauma. This group comprises the large majority of OHCA
345 patients.
346

347 **4.4.1 Inclusion and exclusion criteria for paramedics**

348

349 **Paramedic Inclusion Criteria**

350

- 351 • Employed or soon to be employed by one of the four participating ambulance trusts in general operational
352 duties, and could therefore be despatched to attend an OHCA as the first or second paramedic to arrive at the
353 patient's side.

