534 reporting compression fraction allows heterogeneity between trials to be more consistently described. A suggested
535 mechanism by which SADs may improve outcome from OHCA is a reduction in interruptions to CPR (with an
536 accompanying increase in compression fraction)

537

538 Compression fraction is not routinely measured during OHCA in England, but is technically possible [35].

539 Measurement of compression fraction requires the use of modified defibrillator-monitors, we do not believe it is
540 practical, or affordable, to measure this in all enrolled patients. Instead, we will implement technology that allows
541 compression fraction to be routinely measured during CPR in a sub-set of enrolled patients (for example in one of the
542 four participating ambulance trusts) and collect these data alongside the other outcome measures. This will enable
543 compression fraction to be compared in a subset of the two trial arms, and will also benefit future studies by
544 introducing and evaluating the technology required to routinely measure compression fraction during OHCA.

545

546 **4.7 Sample size calculation**

547

548 In our feasibility study 9% of recruited patients survived to hospital discharge, and this is the current rate of overall
549 survival to discharge reported by English ambulance trusts (see:

550 <http://www.england.nhs.uk/statistics/statistical-work-areas/ambulance-quality-indicators/ambqi-2012-13/>). A 2%
551 improvement in the proportion of patients achieving a good neurological outcome (mRS score of 0-3) would be
552 clinically significant, and similar to the 2.4% difference in survival to discharge between tracheal intubation and SADs
553 reported in a recently published retrospective analysis [18].

554

555 To identify a difference of 2% (8% vs. 10%, i.e. centred on 9%) requires 4,400 patients per group (at the 5% level for
556 statistical significance and 90% power). However, each OHCA is not an independent observation, as the patients are
557 nested within a limited number of attending paramedics. Using data from our feasibility study of 171 paramedics
558 attending 597 OHCA, we estimated the intraclass correlation (ICC) to be <0.001. However, when estimating the
559 sample size we have assumed a conservative estimate for the ICC of 0.005. We estimate that 1,300 paramedics will
560 participate; this gives an adjusted sample size of 4,535 patients per group (9,070 in total). In our feasibility study the

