589 computer based system with secure allocation concealment that cannot be changed once allocated, and will allocate the
590 paramedics in a 1:1 ratio to the two groups.

591

592 Randomisation will be carried out by a member of the CTEU Bristol, or appropriately trained member of the research
593 team.

594

595 Code breaking will not be necessary since paramedics will be aware of their allocation, and whilst the intervention is in
596 progress the allocated treatment will be apparent. Furthermore, once the intervention has been completed subsequent
597 in-hospital treatment is not influenced by study allocation.

598

599 **5.2 Procedures to minimise bias**

600

601 **5.2.1 Selection/allocation bias**

602

603 First, established objectively defined criteria will be used by participating paramedics to determine whether a
604 resuscitation attempt is appropriate, and hence whether the patient is eligible (see standardised resuscitation guidelines,
605 section 4.4.2).

606

607 Second, we will institute a programme of regular monitoring by analysing the proportion of cardiac arrests recruited, to
608 detect any imbalances that may be caused by different thresholds for resuscitation. We will also monitor the presenting
609 rhythm, proportion of witnessed and un-witnessed arrests, presence of bystander CPR and time from 999 call to crew
610 arrival.

611

612 If we suspect that a different threshold for resuscitation is being applied by one or more paramedics participating in the
613 trial, the first step will be to identify the personnel involved and ensure that their training in the trial procedures is up to
614 date, and reinforce the essential messages about the rationale for the trial. The trial team will include a local research
615 paramedic in each of the 4 ambulance regions, this person will develop a close working relationships with the
616 participating paramedics, and will be ideally placed to undertake this role.

617

618 **5.2.2 Blinding**

619

620 Because of the nature of the intervention, ambulance clinicians cannot be blinded, and will be aware of treatment
621 allocations, with an attendant risk of performance bias. However control room personnel will be blinded to the
622 allocation of paramedics, and follow established protocols when allocating resources to a possible cardiac arrest. This
623 will ensure that there is no bias in despatch.

624

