1712 commenced or continued by ambulance staff or responder. For specific inclusion/exclusion criteria and details
1713 of study patients and paramedics see template **Figures F1** and **F2**. 'Trial patients' are those who are
1714 resuscitated, attended by an A2 paramedic and meet the eligibility criteria.

1715 Recruitment over time against targets will be presented by trust and overall (**Figures F3, F4 and F5**).

1716 In the context of this trial, 'advanced airway management' refers to the use of intubation, the i-gel device or
1717 other supraglottic airway devices.

1718 **3.1 Consent**

1719 Due to the emergency nature of the trial, we have ethical approval to enrol patients without consent and seek
1720 consent for further participation from patients who survive to discharge from intensive care (ICU). We have
1721 approval to retain data collected up to the point of approach (or death if this occurs before approach) as well
1722 as mRS at hospital discharge or death for all patients regardless of whether they consent.

1723 Patients may choose one of the following three options when presented with the trial information and consent
1724 form:

1725 Active follow-up - Routine data will be utilised and the patient will be actively followed up at hospital
1726 discharge, and 3 and 6 months after the index OHCA. Quality of life and mRS will be collected at these three
1727 time points.

1728 Passive follow-up - Only routine data will be collected and the patient will not be contacted again about the
1729 study.

1730 Does not wish to participate – No further data collection will take place.

1731 **3.2 Flow of participants**

1732 Participant and paramedic flow will be described via flowcharts (see **Figures F1** and **F2**). Follow-up will
1733 occur at three and six months post OHCA (target ± 4 weeks) for patients who consent to active follow-up.

1734 **3.3 Characteristics of non-study patients**

1735 All resuscitated patients who are attended by an A2 paramedic and meet the eligibility criteria are
1736 automatically enrolled in the study and classed as trial patients. Key demography and initial cardiac arrest
1737 details are collected for all resuscitated patients, including those who are not attended by an A2 paramedic or
1738 are ineligible; these details will be described for trial and non-trial patients (**Table T1**). Resuscitated non-trial
1739 patients are referred to as population 0 in this document.

1740 **3.4 Randomisation**

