1873 quartile range (IQR) if the distribution is skewed), and categorical data will be summarised as a number and
1874 percentage. The summary statistic headings given in **Tables T4** and **T5** are those we expect to use based on a-
1875 priori knowledge of the clinical measurements gained from previous studies. However, if distributional
1876 assumptions are not satisfied, changes will be made.

1877 Statistical tests to compare data not listed as outcomes will not be performed. Secondary outcomes 4
1878 (sequence of airway interventions delivered) and 7 (airway management in place when ROSC was achieved
1879 or resuscitation discontinued) will be described but not formally compared.

1880 **6.2 Primary and secondary outcome data**

1881 **6.2.1 Adjustment in models**

1882 The intention is to adjust the models for the three stratification (design) factors: ambulance trust (four levels),
1883 clinical experience (two levels) and the location of the paramedic’s base ambulance station (two levels) as
1884 fixed effects, and paramedic as a random effect (or a shared frailty term in the time to event model). For the
1885 mRS model where the majority of patients will have a poor outcome/death, the data may be insufficient to
1886 allow estimation of regression coefficients for all these variables. If this is the case, inestimable stratification
1887 variables will be dropped from the model and will be noted in a footnote. For the time to death model, if a cox
1888 model is used the analysis will be stratified by trust (to allow for varying baseline hazards) and adjusted for
1889 the other design factors. If either of the design factors do not meet the proportional hazards assumptions,
1890 stratification by these factors will also be implemented.

1891 **6.2.2 Data presentation and analysis models**

1892 For intention to treat analyses, data will be presented and analysed by the allocated group of the first A2
1893 paramedic on scene, regardless of what airway management the patient received. For per-protocol analyses
1894 (see sections 6.2.5 and 6.2.6), data will be presented and analysed by the allocation of the first advanced
1895 airway management used; if neither i-gel nor intubation was used (or if another SGA was used before an i-gel
1896 or intubation), the patients will be excluded from per-protocol analyses.

1897 All analyses and data presentation will be by intention to treat unless otherwise stated in the Table heading.

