1940 the best fit in terms of information criteria such as AIC, BIC and likelihood ratio tests will be used.

1941 **6.2.3 Statistical significance**

- 1942 For hypothesis tests two-tailed p-values < 0.05 are considered statistically significant.
- 1943 **6.2.4 Model assumptions**
- 1944 For all methods outlined underlying assumptions will be checked using standard methods, e.g. residual plots,
1945 tests for proportional hazards, etc. If assumptions are not valid then alternative methods of analysis will be
1946 sought. If outlying observations are found which mean models do not fit the data adequately, such
1947 observations will be excluded from the main analyses and comments made in footnotes.
- 1948 **6.2.5 Subgroup analyses**
- 1949 Two subgroup analyses for the primary outcome are specified in the protocol: Utstein comparator group vs
1950 non-comparator group and arrest witnessed by ambulance staff or not (**Figure F7**).
- 1951
- 1952 Due to concerns regarding ventilation success raised during the trial, a subgroup analysis of the primary
1953 outcome comparing patients whose i-gel or intubation airway management attempt(s) were or were not
1954 ‘successful’ during the first and/or second attempt (see section 5.2 for definition) will also be performed. This
1955 analysis will be performed per-protocol and as such will only include patients who received at least one
1956 advanced airway management attempt using an i-gel and/or intubation tube.
- 1957
- 1958 Subgroup effects will be fitted by adding a “sub-group x intervention” interaction term to the analysis model.
- 1959 **6.2.6 Sensitivity analyses**
- 1960 For the primary outcome, the following sensitivity analyses will be performed:
- 1961
 - ITT analysis including only patients who received at least one advanced airway management attempt
1962 using an i-gel and/or intubation tube.
 - Per-protocol analysis including only patients who received at least one advanced airway management
1963 attempt using an i-gel and/or intubation tube (see section 6.2.5 for additional sub-group analysis for
1964 this outcome).
 - ITT analysis including all patients who were attended by an AIRWAYS-2 paramedic but not
1965 resuscitated.
- 1966
- 1967
- 1968 **6.2.7 Missing data**
- 1969 In all tables missing data will be indicated by footnotes. If the amount of missing data differs substantially
1970 between treatment groups potential reasons will be explored.
- 1971 Missing predictors:

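### No pre-specified analysis of the primary outcome adjusts for patient case mix, although the covariates are collected and all but age are monitored for recruitment imbalance

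*Protocol*

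**What the plan says.** SAP section 6.2.1 fixes the covariates: "The intention is to adjust the models for the three stratification (design) factors", namely trust, clinical experience and station location, with paramedic as a random effect. All three are attributes of the paramedic, and any that cannot be estimated in the mRS model may be dropped. The three sensitivity analyses in SAP section 6.2.6 change who is included or how patients are grouped. None changes the covariates.

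The patient-level data exist. SAP section 3.3 says that key demography and initial arrest "details are collected for all resuscitated patients, including those who are not attended by an A2 paramedic or" are ineligible. Table T4 describes age, rhythm, witness status, bystander CPR and response times by arm. Rhythm and witness status enter primary-outcome models only through the Utstein and ambulance-witnessed subgroup interactions (SAP section 6.2.5).

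Protocol section 4.3.1 names the threat: unblinded paramedics may recruit different kinds of patients or apply a different threshold for resuscitation. It announces strategies to keep this bias from "occurring, to detect it if it happens, and to correct it if necessary", and refers to sections 4.4.2 and 5.3.7. Section 5.3 ends at 5.3.5. Section 4.4.2 offers review by the DMSC of how often resuscitation is attempted. Section 5.2.1 monitors presenting "rhythm, proportion of witnessed and un-witnessed arrests, presence of bystander CPR and time from 999 call to crew" arrival, and gives as its first step finding and retraining the paramedics concerned.

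**The concern.** Patients enter after their paramedic has been randomised, through staff who know the allocation. If one arm starts resuscitation on a slightly different mix of patients, the arms differ before any airway is placed, and paramedic-level covariates cannot absorb that. Retraining acts on future patients and leaves those already enrolled as they are. If Table T4 then shows an imbalance, any adjusted analysis would be chosen after seeing the data. The second stake is precision: covariates that predict outcome would tighten the primary comparison without new data collection.

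**Working it through.** **1. The plan's own figure.** Protocol section 4.7: "To identify a difference of 2% (8% vs. 10%, i.e. centred on 9%) requires 4,400 patients per group (at the 5% level for" "statistical significance and 90% power". SAP section 6.2.3: "For hypothesis tests two-tailed p-values < 0.05 are considered statistically significant". Allocation (protocol section 5.1) places "paramedics in a 1:1 ratio to the two groups".

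- n = [1.96·√(2·0.09·0.91) + 1.2816·√(0.08·0.92 + 0.10·0.90)]² / 0.02² = 4,301 per group. With continuity correction it is 4,401, which matches 4,400.
- Design effect with ICC 0.005 and 7 patients per paramedic: 1 + (7 − 1)·0.005 = 1.030. Then 4,400 × 1.030 = 4,532, against 4,535 stated.
- Power at 4,535 / 1.030 ≈ 4,403 effective patients per group (no continuity correction): 90.7%.

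The sample size reproduces and assumes no patient covariates.

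**2. Power forgone.** Let R² = var(p(X)) / [p(1 − p)] be the share of outcome variance that the covariates explain. To a good approximation the variance is multiplied by (1 − R²). The documents give no R², so the range is assumed.

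| R² | Power at 4,535 per group | n per group equivalent to the planned size |
|---|---|---|
| 0 | 90.7% | 4,531 |
| 0.05 | 92.0% | 4,305 |
| 0.10 | 93.3% | 4,078 |
| 0.20 | 95.6% | 3,625 |
| 0.30 | 97.5% | 3,172 |

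Simulated logistic regression (1,500 trials per setting, 4,403 per group, Monte Carlo error about 0.7 points) with one prognostic index, unadjusted against adjusted:

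- AUC 0.71: 91.4% against 92.7%
- AUC 0.79: 90.9% against 94.0%
- AUC 0.84: 90.7% against 95.5%
- AUC 0.88: 92.3% against 96.9%

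**3. Effect of an imbalance.** Protocol section 6.2 puts the Utstein comparator group at about 20% of patients, and the overall good-recovery rate is 9%. Assume 25% good recovery in the Utstein group. The rest then have (0.09 − 0.20·0.25) / 0.80 = 5%.

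- Each 1-point difference between arms in Utstein share moves the unadjusted risk difference by 0.25 − 0.05 = 0.20 points. For assumed Utstein rates of 15% to 35% the range is 0.075 to 0.325.
- A 2-point difference from selective recruitment moves it 0.4 points, one fifth of the 2-point target.
- Chance alone, ignoring clustering: 1.96·√(2·0.2·0.8 / 4,535) = 1.65 points of share, or 1.65 × 0.20 = 0.33 points (0.12 to 0.54). This is already in the standard error and is not bias. It is noise that adjustment would take out.
- Utstein status alone gives R² of 0.01 to 0.21 over the same rates, hence power of 91.0% to 95.8%.

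**4. Room for the covariates.** Expected good recoveries: 4,535·(0.08 + 0.10) ≈ 816. Treatment and design factors take 1 + 3 + 1 + 1 = 6 coefficients. Rhythm in three levels (shockable, not shockable, unknown) takes 2, witness status in four levels 3, bystander CPR in three levels 2, and age and response time as linear terms 2. That makes 15, and 816 / 15 ≈ 54 events per coefficient.

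**The case against.** The current primary model is proper. It matches the stratified cluster randomisation, and adding prognostic covariates is a choice of efficiency, not a repair of an error. That stands.

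There are also other safeguards:

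- Enrolment is automatic, with three-source case finding (protocol section 5.6.1), and control-room staff are blinded (section 5.2.2).
- Criteria for withholding resuscitation are objectively defined (section 4.4.2).
- SAP section 6.2.6 includes an ITT analysis that adds patients attended but not resuscitated. This checks a differential resuscitation threshold directly and does not depend on covariates. It does not adjust the resuscitated patients for case mix.

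A reader might infer that the protocol promises covariate adjustment and the SAP breaks that promise. The text does not go so far. It speaks of correction without naming a method, and the only remedy spelled out is retraining. What the documents show is a correction left undefined, with a reference to a section that does not exist.

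Adjustment has limits too. It deals only with measured differences. Rhythm, witness status and bystander CPR come preferentially from Form E1, completed by the unblinded paramedic (SAP section 4). The SAP is already at version 2.0, and a change needs justification and re-approval (SAP section 1.2). These points favour the smaller option in the fix. They do not remove the gap.

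**Conclusion.** The gap is real and of moderate weight. No pre-specified analysis of the primary outcome adjusts for patient-level case mix, in a trial whose own protocol names case-mix differences from unblinded recruiters as a threat.

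A reader might infer that the trial is underpowered as a result. It is not: about 90.7% is reached without covariates. The forgone gain is roughly 1 to 5 points of power, up to about 7 for very strong covariates, and as little as 0.3 points for Utstein status alone at the weakest assumed rate. The shift of about 0.2 points per point of Utstein imbalance rests on the assumed rates of 25% and 5%. No imbalance is known to exist. The statement in protocol section 4.3.1 that chance imbalance will not be a problem is somewhat too strong on these figures, but the planned test stays valid under chance imbalance.

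**What to change.** Before any comparison by group, pre-specify a logistic model with the design factors and paramedic random effect plus presenting rhythm, witness status, bystander CPR, age and 999-to-crew time. Two placements are defensible: as the primary model, with the design-factor model as sensitivity analysis, or at minimum as a named sensitivity analysis in SAP section 6.2.6.

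- **Missing covariates.** SAP section 6.2.7 covers only the randomisation factors as predictors. Use an unknown level for the categorical covariates. That does not work for continuous age and response time, so use simple imputation there (for example the overall mean or median). Nobody is then dropped.
- **Form.** State how age and response time enter the model.
- **Reporting.** Give an adjusted risk difference beside the odds ratio, because the latter becomes conditional on the covariates and is not directly comparable with the design-factor odds ratio.
- **Protocol.** Replace the reference to section 5.3.7 and say what the correction in section 4.3.1 consists of.

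The cost is wording and re-approval, with no new data. The downsides are the conditional odds ratio, reliance on items recorded by the unblinded paramedic, and the fact that only measured imbalance is removed.
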